The administration of intravenous (IV) crystalloid fluids (also known as fluid therapy) is a ubiquitous intervention in patients undergoing surgery. Worldwide, the most commonly used crystalloid fluids available for patients undergoing major surgery include Saline (0.9%), Hartmann's and Plasmalyte solutions. All three solutions are available for IV use at Austin Hospital and considered standard of care for all patients undergoing major surgery. Choice of these fluids amongst anaesthetists at Austin Hospital is similar to worldwide practices. In this study we will be collecting information about intravenous fluid intervention (type of fluid and amount) for adult patients undergoing major surgery (duration >2 hours and at least one overnight stay). Data will be collected over a 12-week period. Specifically, the effects of these fluids on kidney function will be investigated. Perioperative care and fluid intervention therefore will remain completely at the discretion of the treating clinicians.

As this is an observational study, there is no departure from standard care at any stage. It involves the collection of data that has already been collected for clinical or quality assurance purposes.

Whilst the main focus of the study is to investigate the association between these fluids and kidney function, important secondary endpoints that we will collect include changes in electrolytes, post-operative complications, requirements for ICU, requirement for dialysis or hemofiltration, hospital length of stay, and in hospital mortality. All data will be collected from medical records. This study will establish the preliminary evidence base for the design of a larger blinded interventional study (The SPLIT Study, HREC/12/Austin/161), which has been submitted to the Austin Research Ethics Unit and is currently being considered for approval.

The current study will inform clinicians looking after patients undergoing major surgery about the association between these fluids with renal injury.

This study will be also be used in Fulfilment of University of Melbourne BSc Honours Project for [name].

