1.6 Study design

This study aims to observe the association between perioperative intravenous fluids have and renal function in adult patients undergoing major surgery. **It is a single-centered, prospective observational study and therefore does not change the standard of care in any way.** All patients undergoing surgery at Austin Hospital will be given the perioperative fluids at discretion of the treating clinicians.

The study will be conducted over a 12-week period, allowing a wide variety of amount and type of fluids given to the patients. Austin Hospital staff specialists in anaesthesia agree that on the basis of current evidence, Saline (0.9%), Plasmalyte or Hartmann's solution are equally acceptable for crystalloid fluid therapy in every situation requiring major surgery with the exclusion of surgery for liver transplantation where specific hospital perioperative fluid protocols are used in these settings.

As there is no departure from standard care for this study, Saline (0.9%), Plasmalyte and Hartmann's solution will be available for administration to all patients undergoing major surgery. In the situations, where, in the opinion of the treating anaesthetist or clinician, there is a clinical indication for other types of fluid e.g. colloids, blood, dextrose etc, again there will be no deviation from standard care in any way.

All adult patients who undergo major surgery will be analysed. The primary outcome will be the proportion of patients with kidney injury or failure based on established criteria⁵. Secondary outcomes will include delta creatinine (the difference between baseline and peak creatinine), serum electrolyte levels, acid base disturbances, requirements for ICU, duration of ICU stay, hospital length of stay, complications and in-hospital mortality.

All of the data required for this study are collected routinely as part of standard clinical care and/or quality assurance activities⁶.

FLUid intervention and **Renal Outcome Trial** in patients undergoing major surgery: an observational single-centred study (**FLURO TRIAL**). Version 2, 31st Mar 2014

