Potassium (K ⁺), meq/L	4.0 (3.5 to 5.0)	5	0	0
Calcium (Ca ²⁺), meq/L	2.4 (2.3 to 2.6)	0	0	0
Magnesium (Mg ²⁺), meq/L	2.0 (1.4 to 2.4)	3.0	0	0
Acetate, meq/L	0	27	0	0
Gluconate meq/L	0	23	0	0
Lactate, meq/L	1.0 (0.5 to 2.0)	0	0	0
Strong Ion Difference meq/L	44	49	0	0

*All fluids are manufactured by Baxter Healthcare, Toongabie, NSW.

**Median, Reference Range

FEASIBILITY AT AUSTIN HOSPITAL

The departments of Anaesthesia and Intensive Care at Austin Hospital have completed 6 fluid intervention studies, and currently there is one fluid intervention study still underway in the setting of renal transplantation.

Fluid intervention in liver resection

Recently, the authors completed a multicentre randomized double-blind controlled multicentre study of Plasmalyte vs. Hartmann's solution in patients receiving liver resection³². Participants were randomized to Plasmalyte or Hartmann's solution for intraoperative fluid intervention. Primary outcome: base-excess immediately after surgery. Secondary outcomes: lactate levels, strong-ion-difference (SID), total weak acids, net-unmeasured-ions, changes in liver enzymes, perioperative complications and duration of hospital stay.

Results: 60 participants were recruited from 4 tertiary-level hospitals. Both groups were matched according to baseline characteristics, extent of resection, and surgery duration. There were no differences in the volume of trial fluid used, perioperative fluid balance, or urine output. Plasmalyte was not inferior to Hartmann's for the

FLUid intervention and **Renal Outcome Trial** in patients undergoing major surgery: an observational single-centred study (**FLURO TRIAL**). Version 2, 31st Mar 2014

primary endpoint. Plasmalyte base-excess was 0.8mmol/L greater (95%CI: -0.4 to 2.0;P=0.18). This was associated with hyperchloraemia (Difference 1.7mmol/L, 95%CI: 0.2 to 3.2mmol/L, p=0.03) and hyperlactaemia (Difference 0.8mmol/L, 95%CI: 0.2 to 1.3mmol/L; P=0.01) in the Hartmann's group. In the Hartmann's group 23 patients (77%) had a lactate above the reference range compared to 14 patients (47%) in the Plasmalyte group, P=0.02. Complications were more frequent in the Hartmann's Group (56% vs. 20%, 95%CI: 1.3 to 6.1;P=0.007). Median length of hospital stay: 5.9 days vs. 7.8 days (P=0.041) favouring Plasmalyte group.

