1.13 Inclusion criteria

Patients aged ≥ 18 years admitted to the Austin Hospital who receive major surgery. For the purpose of the study, major surgery will be defined as any surgery longer than 2 hours and requiring a least one night of post-operative hospital stay.

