1.15 Baseline data

The following baseline data will be collected:

- Age

FLUid intervention and **Renal Outcome Trial** in patients undergoing major surgery: an observational single-centred study (**FLURO TRIAL**). Version 2, 31st Mar 2014

- Gender
- Admission type (elective vs. emergency)
- Type of surgery (hepatobiliary, colorectal, upper GI, orthopaedic etc.)
- If admitted to ICU: Chronic APACHE co-morbidities (including long-term dialysis)
- If admitted to ICU: APACHE-III admission diagnosis⁴²
- If admitted to ICU: Illness severity based on the on the APACHE-III risk of death score⁴²
- Baseline creatinine.
- Baseline biochemistry

(Note: - all of these data are routinely collected for quality assurance purposes or as measured as part of usual clinical care)

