1.26 Analysis plan

A complete description of the statistical analyses will be specified in a statistical analyses plan, finalised prior to completion of the study.

All analyses will be conducted on an intention-to-treat basis.

The primary analyses will be unadjusted analyses in which binary outcomes will be compared using relative risks with 95% confidence intervals and chi square tests and continuous outcomes will be compared with the use of mean differences and unpaired T-tests assuming that normality assumptions are met. If normality assumptions are not met then we plan to attempt simple data transformation, such as a logarithm transformation, and if this fails to proceed to a Mann-Whitney rank based test. Adjusted analyses will be performed using Poisson regression for binary

FLUid intervention and **Renal Outcome Trial** in patients undergoing major surgery: an observational single-centred study (**FLURO TRIAL**). Version 2, 31st Mar 2014

outcomes and linear regression for continuous outcomes. Baseline covariates will include age, gender, elective vs. emergency surgery, surgical specialty of admission, type of operation, and baseline serum creatinine level. Survival times will be compared using log-rank tests and presented as Kaplan-Meier curves. Multivariable models will be developed to study the predictors of AKI and the independent association between fluid choice and renal outcomes.

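### Duration of surgery decides eligibility but is neither listed for recording nor named as a covariate, so the adjusted fluid association may keep confounding that could cheaply be removed

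*Protocol*

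**What the plan says.** Section 1.13 of the Protocol makes eligibility depend on operating time: "major surgery will be defined as any surgery longer than 2 hours and requiring a least one night of post-operative hospital stay". The synopsis repeats the threshold and describes the exposure as "intravenous fluid intervention (type of fluid and amount) for adult patients undergoing major surgery (duration >2 hours and at least one overnight stay". Section 1.6 says how fluid is assigned: "All patients undergoing surgery at Austin Hospital will be given the perioperative fluids at discretion of the treating clinicians".

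Section 1.15 lists the baseline data. The surgical items are admission type and "Type of surgery (hepatobiliary, colorectal, upper GI, orthopaedic etc"; operating time is not among them. Section 1.21 names the only items that are not routinely collected, which are fluid bolus volumes and renal outcome data. It does not mention duration either.

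Section 1.26 gives the covariates for the adjusted Poisson and linear models: "Baseline covariates will include age, gender, elective vs. emergency surgery, surgical specialty of admission, type of operation, and baseline serum creatinine level". The synopsis has the same six. Section 1.26 then adds a further aim: "Multivariable models will be developed to study the predictors of AKI and the independent association between fluid choice and renal outcomes".

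**The concern.** In a study without randomisation, the covariate list carries the whole defence of the adjusted result. Duration is a plausible predictor of postoperative AKI, and the amount of fluid given can be expected to rise with it. The 2-hour rule sets a floor but no ceiling, so duration can vary widely within a class such as colorectal or orthopaedic surgery. Operation type is therefore an incomplete stand-in.

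The investigators themselves treat duration as something on which fluid groups should be comparable. Reporting their randomised liver resection trial in the feasibility section, they write: "Both groups were matched according to baseline characteristics, extent of resection, and surgery duration". Here no randomisation balances it.

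What is at stake is how far the association described as independent can be read that way, and whether the AKI prediction model omits an obvious candidate.

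**Working it through.** The plan states no figure on this point, so there is none to reproduce. The check has two parts.

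**1. Where duration appears**

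| Place in the Protocol | Duration of surgery |
|---|---|
| Synopsis and 1.13, eligibility | Yes, as the threshold of more than 2 hours |
| 1.15, baseline data | Not listed |
| 1.21, items outside routine collection | Not listed |
| Synopsis and 1.26, covariates | Not among the six named |
| 1.26, multivariable models | No further covariates named |

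**2. How much it could matter**

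Treat duration as a two-level variable, long or not long. Let R be the AKI risk ratio for long operations. Let p1 and p0 be the proportions of long operations in saline patients and in other patients, *within strata of the covariates already listed*. Leaving duration out multiplies the fluid relative risk by

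B = [1 + p1(R − 1)] / [1 + p0(R − 1)].

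R, p1 and p0 are all assumptions; the documents give none of them.

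| R | p1 | p0 | B |
|---|---|---|---|
| any | 0.5 | 0.5 | 1.00 |
| 1.5 | 0.5 | 0.4 | 1.25/1.20 = 1.04 |
| 1.5 | 0.5 | 0.3 | 1.25/1.15 = 1.09 |
| 2 | 0.5 | 0.3 | 1.5/1.3 = 1.15 |
| 2 | 0.3 | 0.5 | 1.3/1.5 = 0.87 |
| 3 | 0.6 | 0.3 | 2.2/1.6 = 1.38 |
| 3 | 0.3 | 0.5 | 1.6/2.0 = 0.80 |

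For scale, the planning rates in section 1.25 give a relative risk of 14/8.4 = 1.67. With R = 2 and long operations in 50% against 30%, a true 1.00 would appear as 1.15, and a true 1.67 as 1.67 × 1.154 = 1.92. With the imbalance reversed, the same true 1.67 would appear as 1.67 × 0.867 = 1.44.

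**Cost in parameters.** At the planning rates, the expected number of AKI events lies between 400 × 0.084 = 34 and 600 × 0.14 = 84. One continuous term uses one degree of freedom, fewer than a multi-level operation-type factor that is already planned.

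**The case against.** - **This belongs in the statistical analysis plan.** Section 1.26 defers the full description to that plan, its covariate wording is not exhaustive, and the multivariable models have no closed list. Duration could enter later without contradicting anything. That is fair, and it means the Protocol contains no contradiction here. But the Protocol does more than defer: it names a covariate list twice without duration. A later plan can use only what was recorded.
- **Section 1.15 is a baseline list.** Actual operating time is intraoperative and would not be expected there. Fluid volumes and postoperative creatinine are also absent from it, though the study plainly collects both. This stands: a reader might infer that duration will not be kept, but the documents show only that it is not listed.
- **No imbalance is shown.** A reader might infer that the fluid groups differ in operating time, or that a saline effect would be inflated. No section says so. Section 1.6 reports that staff regard the three crystalloids as equally acceptable for all major surgery except liver transplantation. That does not establish balance, since preferences can still vary with the case, but it gives no ground for asserting imbalance or its direction.
- **The listed covariates absorb part of it.** Section 1.26 lists specialty and operation type separately, so operation type may be finer than the classes in section 1.15. This stands: only the difference left within strata matters.
- **Duration arises after fluid has started.** For crystalloid type this needs only a short justification, because there is no evident route from choice of crystalloid to operating time. The comparable durations in the randomised liver resection trial fit that view, although it had 60 participants and no saline arm. For amount of fluid the objection has more force, because intraoperative events may affect both volume and duration.

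**Conclusion.** The point holds as an avoidable gap in a stated covariate list. Duration must be established for every included patient, is plausibly prognostic, and is missing from the adjustment in a comparison that depends on adjustment.

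Whether this produces bias rests on one condition: duration must be related both to fluid and to AKI within strata of operation type, specialty and urgency. The documents cannot show whether that is so. The factor of 0.80 to 1.38 is the span of the assumed scenarios, not an estimate; it runs in both directions and is 1.00 under balance.

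The reach is limited to the adjusted analyses and the multivariable AKI models. The primary analysis is unadjusted and carries any difference in duration with or without the change. A reader might also infer that duration could take the place of surgical specialty. The documents give no reason to drop a prespecified covariate, and adding one term does not require it.

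**What to change.** 1. List duration of surgery (hours) for recording as an intraoperative variable, alongside the data in section 1.15.
2. Add it as a continuous covariate to the adjusted analyses and to the multivariable AKI models, in section 1.26 and in the synopsis. Keep surgical specialty.
3. Add one sentence to section 1.26 stating that crystalloid type is not expected to determine operating time, so that duration is treated as a confounder or prognostic factor and not as a mediator.
4. Where amount of fluid is the exposure, report results with and without duration, because its causal position is less clear there.

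The cost is one field that already has to be ascertained for eligibility, one model parameter, and a covariate that is not strictly baseline and so needs the justification in step 3. Patient care and the unadjusted primary analysis are unaffected.

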1.3 Coordinating Department

Department of Anaesthesia
Austin Hospital
Heidelberg, Victoria
Australia

STUDY SYNOPSIS

Title:	Fluid intervention and Renal Outcome Trial in patients undergoing major surgery: an observational single-centred study (FLURO Trial).
Short Title:	Fluid therapy in major surgery.
Design:	Single-centred, prospective observational study. Information about intravenous fluid intervention (type of fluid and amount) for adult patients undergoing major surgery (duration >2 hours and at least one overnight stay) will be collected over a 6-week period. The effects of these fluids on renal function will be investigated.
Study Centers:	1
Hospital:	Austin Hospital
Study question:	What are the association between perioperative intravenous fluids and renal function in adult patients undergoing major surgery at a University teaching hospital.
Study Objectives:	To determine the association between perioperative intravenous fluids and renal function in adult patients undergoing major surgery.
Primary Outcome:	Acute kidney injury (AKI), defined by an increase in creatinine greater than 25% or 0.5 mg/dL (44 µmol/L) from baseline to peak value within the first 72-hours postoperatively.
Secondary Outcomes:	Serum electrolytes Acid base disturbances Post-operative complications Requirements for ICU Requirement for dialysis or hemofiltration Duration of ICU stay Hospital length of stay In-hospital mortality
Inclusion criteria:	Adult patients ≥ 18 years Elective or emergency surgery Surgery duration > 2 hours Requiring at least one overnight stay
Exclusion criterion:	<18 years in age Liver transplantation
Number of planned Subjects:	400-600

FLUId intervention and **Renal Outcome Trial** in patients undergoing major surgery: an observational single-centred study (**FLURO TRIAL**). Version 2, 31st Mar 2014

Investigational product:	Nil
Safety considerations:	
This is an observational study only. There is no departure from standard care at any stage. It only involves the collection of data that has already been collected for clinical or quality assurance purposes.
 
Perioperative care and fluid intervention will remain completely at the discretion of the treating clinicians.

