1.9 Number of participants

Given the current theatre workload at Austin Hospital, 400-600 participants will be recruited.

FLOW DIAGRAM

RESEARCH QUESTION

What is the association between perioperative intravenous crystalloids with renal function in adult patients undergoing major surgery at a University teaching hospital?

BACKGROUND AND RATIONALE

For all patients undergoing major surgery, two important and fundamental goals in fluid intervention include the maintenance of intravascular volume to ensure optimal organ perfusion and function, and the avoidance of metabolic and electrolyte disturbances that can compromise organ function.

Worldwide, the most commonly used crystalloid fluids available for all patients undergoing surgery include:

1. Hartmann's solution
2. Saline (0.9%)
3. Plasmalyte solution

The electrolyte composition of some of these commonly used crystalloid fluids are summarised in Table 1. All these solutions have similar sodium concentrations (130-150 mmol/L) and may contain physiological concentrations of potassium (Hartmann's and Plasmalyte solutions). There are however some major differences in anion composition. All three solutions above have chloride as a major anionic constituent, the balance in Hartmann's and Plasmalyte solutions being made up of lactate and acetate respectively. Both lactate and acetate are ultimately metabolised by the liver to bicarbonate, thus producing a near ideal physiological solution. Because their electrolyte composition is similar to plasma, they are frequently called "balanced" crystalloid solutions.

Pre-clinical and early clinical data suggest that saline may give rise to adverse effects including immune dysfunction⁷, gastrointestinal dysfunction⁸ and decreased renal cortical perfusion and renal blood flow⁹. There is strong expert opinion that 'normal saline' or Saline (0.9%) is neither "normal" nor "physiological"¹⁰. In fact, it has approximately 1.5 times more chloride than normal plasma and its use can lead to hyperchloraemic acidosis³. Although hyperchloraemic acidosis may be a benign phenomenon^{11,12}, recent data raise the possibility that the use of saline for fluid resuscitation in adult ICU patients may lead to an increased risk of developing acute kidney injury compared to resuscitation fluids with a lower concentration of chloride such as Plasmalyte^{2,13}.

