1.10 Summary

This is an observational study; there is no departure from standard care at any stage. It involves the collection of data that has already been collected for clinical or quality assurance purposes.

In this study we will be collecting information about intravenous fluid intervention (type of fluid and amount) for adult patients undergoing major surgery (duration >2 hours and at least one overnight stay). Data will be collected over a 12-week period. Specifically, the association of these fluids with kidney function will be investigated. Perioperative care and fluid intervention therefore will remain completely at the discretion of the treating clinicians.

The current study will inform clinicians looking after patients undergoing major surgery about the effects of these fluids on renal injury.

This study will be also be used in Fulfilment of University of Melbourne BSc Honours Project for [name].

FLUid intervention and **Renal Outcome Trial** in patients undergoing major surgery: an observational single-centred study (**FLURO TRIAL**). Version 2, 31st Mar 2014

OBJECTIVES

The overall objective of this study is to determine the association between perioperative intravenous fluids and renal function in adult patients undergoing major surgery.

The choice of perioperative intravenous fluid intervention such as Saline (0.9%) vs. Plasmalyte vs. Hartmann's solution will be entirely at the discretion of the all clinicians caring for the patients.

Specifically, we aim to establish the association of Saline (0.9%), Plasmalyte and Hartmann's solution on:

1. The development of acute kidney injury in hospital
2. The development of biochemical and acid-base derangements
3. The development of postoperative complications
4. Requirements for ICU
5. Requirement for dialysis or hemofiltration
6. Duration of ICU stay
7. Hospital length of stay
8. Hospital mortality

STUDY DESIGN

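### Kaplan-Meier and log-rank analysis of survival times does not suit a mortality outcome observed only in hospital: censoring at live discharge would be informative

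*Protocol*

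**What the plan says.** The analysis plan in protocol section 1.26 states without condition: "Survival times will be compared using log-rank tests and presented as Kaplan-Meier curves". It gives no time origin, horizon or censoring rule for these survival times, and no survival-time endpoint is defined elsewhere.

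Wherever death appears as an outcome, it is death in hospital:
- Study Synopsis, secondary outcomes: "Hospital length of stay In-hospital mortality".
- Section 1.6: "hospital length of stay, complications and in-hospital mortality".
- Objectives, last item: "Hospital mortality".
- Lay Summary: "hospital length of stay, and in hospital mortality. All data will be collected from medical records".

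The list of secondary outcome measures in section 1.17.2 omits mortality. Neither the Lay Summary nor section 1.21 on data collection mentions contact after discharge, a vital-status check or linkage to a death register.

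For binary outcomes, section 1.26 already names relative risks with confidence intervals and chi-square tests, with Poisson regression for the adjusted analysis.

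**The concern.** Kaplan-Meier and log-rank methods assume that a patient censored at time t has the same later risk of death as a patient still under observation at t. Live discharge breaks this assumption, because patients go home when they have recovered. Censoring them there lets the sicker patients who remain in hospital stand in for them.

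There are two consequences. First, the curve overstates the proportion who die in hospital. Second, if one fluid group leaves hospital sooner, its risk set shrinks faster, each death weighs more, and that group looks worse on the log-rank test even when the same proportion dies.

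Length of stay is itself a study outcome. Fluid choice is left to clinicians, so case mix alone could make stay differ between groups, and the log-rank test does not adjust for it.

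**Working it through.** The protocol gives no mortality rate, number of deaths or hazard ratio, so there is no figure of its own to reproduce. The check asks what the named method yields when true in-hospital mortality is equal in both groups and survivors are censored at discharge.

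**Inputs from the protocol.** Sample size, section 1.9: "400-600 participants will be recruited". Illustrative stays, from the liver-resection trial described under Feasibility at Austin Hospital: "Median length of hospital stay: 5.9 days vs. 7.8 days (P=0.041) favouring Plasmalyte group".

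**Assumed inputs.** In-hospital mortality p of 2% or 5%; log-normal stay with log-SD 0.6 to 0.9; two equal groups; two-sided 5% test. Deaths are timed in one of two ways: (A) like stays, or (B) identically in both groups, as 0.5 day plus an exponential with mean 6 days, capped at day 30.

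**Step 1: level of the curve, by hand.** Under timing A, let S(t) be the proportion still in hospital at t. The hazard of death is p times the hazard of leaving hospital, so:
- the Kaplan-Meier estimate of death tends to 1 − S(t)^p;
- the true cumulative incidence is p × (1 − S(t)).

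With p = 0.02 and log-SD 0.7, S(t) = 1 − Φ(ln(t/median)/0.7):

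| Day | Median stay | S(t) | Kaplan-Meier death | True in-hospital death |
|---|---|---|---|---|
| 14 | 5.9 | 0.109 | 1 − 0.109^0.02 = 4.3% | 1.8% |
| 14 | 7.8 | 0.202 | 1 − 0.202^0.02 = 3.1% | 1.6% |
| 30 | 5.9 | 0.010 | 1 − 0.010^0.02 = 8.8% | 2.0% |
| 30 | 7.8 | 0.027 | 1 − 0.027^0.02 = 7.0% | 1.9% |

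Simulation of the same set-up agrees: 8.8%-9.0% vs 7.1% at day 30. Over both timings and the log-SD range, a true 2% appears as about 3%-5% at day 14 and 4%-15% at day 30.

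**Step 2: comparison between groups.** Under timing A the ratio of death hazards equals the ratio of discharge rates, so the log-rank test in effect compares speed of discharge. The simulated hazard ratio is 1.44 (log-SD 0.7) against the group with the shorter stay.

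Timing B is stricter, because only survivors' discharge times differ. With log-SD 0.6 the hazard ratio is about 0.74 for longer vs shorter stay, or 1/0.74 = 1.35 the other way. False-positive rates over 4,000 runs per scenario were:

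| Median stays | Mortality | N = 400 | N = 600 |
|---|---|---|---|
| 6 vs 6 | 2% | 4.6% | 4.9% |
| 6 vs 6 | 5% | 4.9% | 4.6% |
| 5.9 vs 7.8 | 2% | 8.3% | 8.6% |
| 5.9 vs 7.8 | 5% | 10.5% | 12.5% |

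Over both timings and log-SD 0.6-0.9, the spurious hazard ratio is about 1.2-1.5 and the false-positive rate about 6%-19%. The upper end is approximate: a repeat of the most adverse corner (timing A, log-SD 0.6, 5% mortality, N = 600, 3,000 runs) gave about 22%.

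**Step 3: alternatives on the same timing-B data (including an assumed wider gap of 5 vs 10 days).** The chi-square test on in-hospital death rejected in 4.3%-5.4% of runs. The log-rank test with discharged survivors kept at risk to day 30 rejected in 4.2%-5.3%. Both hold the nominal level.

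**The case against.** The strongest reply is that the protocol nowhere says patients are censored at discharge. A censoring rule is ordinary content for the statistical analysis plan, to which section 1.26 defers the full description. A reader might infer that survival times can only be censored at discharge. The documents do not support that: step 3 shows that the same log-rank test behaves correctly if discharged survivors stay in the risk set to a fixed day, and this needs no new data. The bias is therefore conditional on the usual application. What remains is that the protocol itself fixes the method, and the planned data do not support its standard use.

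A reader might also infer that length of stay is expected to differ by fluid. The protocol makes no such prediction for this cohort. The 5.9 and 7.8 days come from 60 liver-resection patients given Plasmalyte or Hartmann's, whereas this study takes all major surgery, and its power statement compares saline with other crystalloids. With equal stays the test keeps its size.

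Finally, in-hospital death is a binary outcome, so the relative risk in section 1.26 would be reported beside the curve. At an assumed 2%, 400-600 patients give only 8-12 deaths, and the excess of false positives is then modest. Both points stand and limit the weight of the finding.

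**Conclusion.** The concern holds as a point on a secondary outcome. Section 1.26 names a survival method for an endpoint observed only until discharge, and the usual way of applying it makes censoring informative. The overstatement of mortality needs only censoring at discharge. The false difference between fluids also needs unequal stays; for the illustrative 5.9 vs 7.8 days it has the size shown above, and it runs against the group discharged sooner. These figures rest on assumed mortality, spread of stay and timing of death.

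Two stronger readings are not supported. A reader might conclude that a benefit on length of stay could reverse the study's mortality conclusion. Nothing in the protocol makes the log-rank test the basis of that conclusion, and the planned relative risk is free of this bias. Nor should the day-30 inflation be taken as typical of the whole curve: in the step 1 example only about 1% and 3% of patients are still in hospital by then, and the overstatement at day 14 is much smaller.

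The primary analysis of acute kidney injury is unaffected.

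**What to change.** Replace the survival-time sentence in section 1.26 with a comparison of in-hospital death as a binary outcome: relative risk with 95% confidence interval, and the adjusted Poisson model already named there. With few deaths the adjusted estimate will be imprecise and should be presented as such.

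If a display over time is wanted, show the cumulative incidence of in-hospital death with live discharge as a competing event. Keeping discharged survivors in the risk set to a stated fixed day is equivalent, because every stay ends in an observed death or discharge. Label the result as in-hospital death, not survival.

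The cost is one sentence in the protocol or the statistical analysis plan. No extra data are needed, since stay and in-hospital death are already collected.
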